## **Baseline Visit**

### **D.3. Baseline Visit**

When interested subjects are scheduled for the baseline clinic visit, they will be mailed a medical clearance form which will have been signed by their healthcare provider. The signed clearance form must be faxed or submitted to study staff prior to randomization and assignment to a study arm. At the baseline study visit, we will review the participant's medical history and obtain information about demographics, cigarette use, and prior participation in pulmonary rehabilitation. Comorbidities of coronary artery disease, congestive heart failure, diabetes, and other diagnoses that affect the lower limbs (osteoarthritis or degenerative joint disease, hip or knee replacements, rheumatoid arthritis, chronic low back pain, lumbar spine disease, peripheral vascular disease, or peripheral neuropathy) will be noted. We will record medication use and current use of supplemental oxygen. We will also assess history of AEs and related medication use in the previous 12 months since prior AE strongly predicts future AEs (83). Weight and height will be measured for the calculation of body mass index (BMI). Baseline data will characterize the cohort and allow analysis of potential confounders.

We will verify the accuracy of the pedometer in each subject by comparing measured to manually counted steps during a standardized in-clinic walk of 244 meters. Subjects can use assistive devices such as a cane if they typically use one for walking. Only persons in whom the pedometer has >90% accuracy in capturing step counts will be eligible. Eligible subjects will perform 6MWT, spirometry, HRQL assessment with the SGRQ and Veterans SF-36, and dyspnea assessment with the UCSD Shortness of Breath Questionnaire and MMRC Dyspnea Scale (Assessments described in D.6). Subjects will also complete the Barriers to Exercise Questionnaire, Physical Recall Activity Questionnaire, Bristol's COPD Knowledge Questionnaire, Exercise Self-Regulatory Self-Efficacy Questionnaire, Beck Depression Inventory, Epworth Sleepiness Scale, CHAMPS Physical Activity Questionnaire, MOS Social Support Survey, Dietary Questionnaire, and the Brief Pain Inventory (short form). If a subject does not have time during the study visit to complete the study-related questionnaires, we will contact the subject by phone to finish the questionnaires by phone at a time after the visit or send the questionnaires home with the subject to be completed and sent back in a pre-paid mailer. Three tubes of blood (2 tablespoons) will be drawn by venipuncture, overnight shipped to Massachusetts Veterans Epidemiology Research and Information Center (MAVERIC) at VA Boston, and processed and stored for biomarker analyses. Subjects recruited at VA Boston will be asked to complete a DXA scan to measure body composition and bone mineral density at the baseline screening visit. Additionally, subjects will be asked to complete a body composition reading using the Omron Fat Loss Monitor (model HBF-306CN) for comparison of body fat measurements between measurement methods. The Omron Fat Loss Monitor is a portable handheld device that the

participant grips while in a seated position for 5-10 seconds. Three readings will be taken in this fashion and will be completed in <10 minutes. The device has been approved for use in the general population except in individuals who are pregnant and who have implanted medical devices such as pacemakers and defibrillators. Although independent studies have suggested that bioimpedance monitors are safe for use in individuals with pacemakers, we will exclude any subject who has a pacemaker or defibrillator from the bioimpedance measurement. Subjects who are pregnant are excluded from both the DXA and bioimpedance measurements. If subject has undergone a DXA scan at the VA Boston Osteoporosis Clinic previously within 6 months, then the data from the Osteoporosis Clinic may be used and subject does not need to complete a scan specifically for the research study. If the DXA scan is not completed, then the body composition reading using the Omron Fat Loss Monitor (model HBF-306CN) will not be completed.

It is expected that some subjects may be unable to complete all the proposed assessments during the study visits. Furthermore, subjects may refuse to complete any portion of the study assessments.

Research staff will set up Fitbit Zip pedometers for all subjects who are eligible and require a 10-day baseline collection. All subjects will be sent home to wear the pedometer for 10 days to assess baseline level of walking. They will be given detailed instructions on use of the pedometer, which will include instructions on how to download the Fitbit Connect software so they can upload their step count data at home and a prepaid mailer to return the Fitbit Zip if they are randomized to the control arm after baseline step count collection. This account setup will be for uploading the data to the study team and will not include any access to the Fitbit website by the subjects. Subjects will only be able to access their step counts through the study website if randomized to the intervention. The Fitbit Zip pedometer will have a sticker covering the digital display to prevent feedback. Subjects will be instructed to perform their *usual* physical activities and exercise. Subjects will provide the phone number which they will use to receive the randomization assignment.

## **Randomization**

After collecting 10 days of baseline step counts, subjects will upload their step count data using the Fitbit Connect Software by placing their pedometer near the dongle device connected to their computer, or through Bluetooth (whichever works for their computer system). Study staff will be available to assist subjects navigate any issues with uploading. In addition to obtaining representative baseline step-count data, this run-in period will allow us to gauge subject compliance with wearing the pedometer if assigned the intervention, potentially reducing the number of drop-outs. Participants must have  $\leq 3$  no-wear days (<200 steps per day) to be eligible to be randomized. Medical clearance will have been obtained from a healthcare provider. Eligible subjects will be randomized to 1) written instructions and education to exercise (usual care) or 2) pedometer and Internet-mediated walking program. Since the sample size is relatively small, we will use blocked randomization, and a computer-generated sequence of random numbers, with the allocation scheme concealed and unpredictable. Study staff will call the participant to inform him/her of the assignment. Subjects who are randomized to intervention will choose a username and password that allow them to log in to the study website to upload their step counts. Study staff will help participants choose strong username and passwords to optimize privacy and security. Subjects who are randomized to the control arm will be asked to return the pedometer in the prepaid mailer provided and will be informed of the pedometer wear schedule and reminded that they will receive the pedometer to keep at the conclusion of study participation. To ensure blinding, study staff communicating randomization assignments to subjects will be different from study staff conducting follow-up assessments.

*Written instructions and education to exercise (Usual care, Appendix 1)*

Using a standardized script at the randomization phone call, study staff will deliver verbal instructions to all subjects to encourage participants to increase one's walking slowly and steadily, and to increase the amount of exercise each week. Exercise is defined as planned PA in addition to activities performed as part of one's daily routine. Daily PA is all PA performed, including exercise. Increasing daily PA and exercise are goals of the program. Exercise can be mainly walking in the community or using exercise equipment at a local gym. We intentionally do not specify duration or intensity of exercise both to mirror usual care and to avoid any confusion with walking goals instructed by the WEB intervention. Adapted written materials from [name] (on our DSMB), which are currently used at the University of Washington and VA Boston, reinforce the verbal instructions. All subjects will receive this 42-page booklet (Appendix 1) with information about cardiovascular endurance and strengthening exercises, an action plan for identifying symptoms of a COPD AE, and how to resume exercise after a COPD AE. The written booklet also contains information about oxygen use during exercise and available resources for smoking cessation. To enhance treatment fidelity (see D.8) and to measure compliance with the study, subjects will receive exercise logs in which they will track whether they exercised each day (Appendix 2). The next instance that participant will have contact with study staff will be at a clinic visit 3 months following the baseline visit.

Research staff at the University of Michigan will maintain the website on their computer servers. [name] and her staff will finalize content and develop specifications of the website for dedicated use with the proposed protocol, beta-test the specifications, monitor step-count data during the intervention phase, maintain the Web-based applications for the intervention, and provide data from the website for analyses.

The specific items involved with developing, testing, and maintaining the website include:

- Procurring, managing and securing database and Web servers, system-level software and site/user licensing required to run the system.
- Ongoing management and maintenance of the system and system security throughout the study.
- Performing website modifications for automated weekly step-count feedback, and educational and motivational messages.
- Designing website so that subjects who are current oxygen users or active smokers will receive tailored messages about oxygen use during exercise or smoking cessation.
- Beta testing website prior to launch and routine regular maintenance.
- Providing back-up of study data. This task also includes automated backup software and scheduling, as well as obtaining and securely storing physical backup media.
- Providing study staff access to the study data systems as needed for study implementation.
- Capturing, maintaining, and securing delivery of step-count data for analysis.
- Capturing and reporting data on frequency of website use. Each time a participant logs in, or uses a link, an automated digital log entry occurs.

There is no other website currently available that has all the unique components offered by WEB (feedback, individualized goals, and educational content and motivational messages).

### D.5. Follow-up Clinic Visits and Phone Calls

Follow-up clinic visits will be conducted when subjects are in stable clinical status, where at least 2 weeks have elapsed since the time of their last prednisone or antibiotic course for treatment of a COPD exacerbation. Participants in both arms will be seen in our research clinics at months 3, 6, and 12 (Table 5). At each follow-up visit, study staff will remind participants not to disclose treatment arm. Subjects will be reminded that they should be working to slowly and steadily increase their walking and exercise. Subjects will perform 6MWT, spirometry, and HRQL assessments. All changes in medication or clinical status will be noted, any potential adverse events recorded, and a history of any COPD exacerbations or hospitalizations in the previous 3 months ascertained. We will also assess dyspnea (UCSD Shortness of Breath Questionnaire and MMRC Scale), physical activity (CHAMPS and [name]), and depression (Beck Depression Inventory). Subjects will also complete the following questionnaires: the Barriers to Exercise, Physical Activity Recall, VR-36, MOS Social Support, Bristol's COPD Knowledge, Exercise Self-Efficacy, Epworth Sleepiness Scale, the Brief Pain Inventory (short form, administered at C03, C06 and C12), and the Dietary Questionnaire (only administered at C00 and C12). The intervention subjects will also complete the Intervention Feedback Questionnaire that asks about the subject's experience with the study website and pedometer at the 6-month and 12-month in-clinic study visits. Blood for inflammatory biomarkers will be drawn by venipuncture, packed in a shipping container with an ice pack, and transported to the MAVERIC blood lab for processing and storage. Subjects recruited at VA Boston will be asked to complete DXA scans for body composition and bone mineral density at the 12-month in-clinic visit, and additionally will be asked to complete a body composition measurement using the Omron HBF-306CN. We will exclude any subject with a pacemaker or defibrillator to minimize any potential risks. If subject has previously undergone a DXA scan at the VA Boston Osteoporosis Clinic within 6 months, then the data from the Osteoporosis Clinic may be used and subject does not need to complete a scan specifically for the research study. If a subject does not complete the study-related questionnaires during the in-clinic visit, research staff will contact the subject after study visit by phone to finish the questionnaires over the phone or send the questionnaires home with the subject to be completed and returned in a pre-paid mailer.

To objectively measure engagement in PA, the pedometer will directly measure 14 days of walking of subjects in both arms. To assess treatment fidelity, exercise logs will be collected from subjects each month. Participants will be contacted by telephone at month 9. They will provide an interim history of home exercise and answer questions about symptoms, medications, AEs, and hospitalizations that occurred during the prior 3 months. Subjects will also receive a mailing with questionnaires (Barriers to Exercise, Physical Activity Recall, SGRQ, VR-36, UCSD SOB, Bristol's COPD Knowledge, Exercise Self-Efficacy, CHAMPS Physical Activity, Beck Depression Inventory, and Exercise Logs) to complete at home. At any time, if a subject experiences a medical problem that prevents walking and exercise, s/he will be suspended from the study. S/he will resume the study when s/he has returned to baseline clinical status.

It is expected that some subjects may be unable to complete all the proposed assessments during the study visits. Furthermore, subjects may refuse to complete any portion of the study assessments.

**Table 5:** Schedule of Clinic Visits (C), Telephone Calls (P), and Assessments (both study arms)

	Baseline C00	Month 3 C03	Month 6 C06	Month 9 P09	Month 12 C12
Medical and Exercise History	X	X	X	X	X
6-Minute Walk Test	X	X	X		X
Barriers to Exercise Questionnaire	X	X	X	X	X
Physical Activity Recall Questionnaire	X	X	X	X	X
HRQL SGRQ	X	X	X	X	X

Veterans SF-36 HRQL	X	X	X	X	X
MOS Social Support Questionnaire	X	X	X		X
MMRC	X	X	X		X
UCSD SOB	X	X	X	X	X
Spirometry	X	X	X		X
Blood Draw for Biomarkers	X	X	X		X
Beck Depression Inventory	X	X	X	X	X
CHAMPS Physical Activity Questionnaires	X	X	X	X	X
Bristol's COPD Knowledge	X	X	X	X	X
Exercise Self Efficacy	X	X	X	X	X
Epworth Sleepiness Scale	X	X	X		X
Brief Pain Inventory (Short form)	X	X	X		X
Intervention Feedback Questionnaire (Intervention arm only)			X		X
Dietary Questionnaire	X				X
Exacerbation, Adverse Event Monitoring, and Hospitalization History	X	X	X	X	X
Daily Exercise Logs	X	X	X	X	X
Daily Step Count	X	X	X	X	X
DXA Scan (VABoston site only)*	X				X
Body Composition/Bioimpedance (VABoston site only)	X**				X**

*If subject has previously undergone a DXA scan at the VA Boston Osteoporosis Clinic within 6 months, then the data from the Osteoporosis Clinic may be used and subject does not need to complete a scan specifically for the research study.
 
**Contingent upon DXA scan being completed. If a DXA scan is not completed during the C00 or C12 study visits, the body fat composition/bioimpedance measurement will not be completed.
					

**D.6. Short- and Long-Term Outcome Assessments:** All tests will be conducted by study staff, technicians, or physicians who are blinded to treatment assignment.

**Primary Outcome: Exercise capacity:** Exercise capacity will be assessed with maximal distance walked on the 6MWT, performed according to ATS guidelines (80). Both sites currently have a designated course in the hospital corridor and standardized prompts to perform the 6MWT as part of the NHLBI LOTT protocol. In general, persons will be asked to cover as much distance as possible in 6 minutes, and the distance walked will be recorded. Subjects can use assistive devices, such as a cane, if they typically (more than half the time) use one for walking. Subjects will use supplemental oxygen if already prescribed oxygen for use during physical activity. If hypoxemia, oxygen saturation <85%, is observed at the end of the 6MWT, subjects will be temporarily excluded from further study participation and their primary provider contacted for further care. These subjects can be reassessed for eligibility at a later date. Hypoxemia and dyspnea predict balance impairment and falls in COPD (89); both will be assessed by study staff immediately preceding the 6MWT. Also, the 6MWT will not be performed if the subject is unsteady on his feet during the initial short walk used to assess pedometer accuracy, and demonstrates a high risk of falling. Staff performing the 6MWT will be trained in Basic Life Support. Emergency treatments, including nebulizer therapy, an automated external defibrillator, and a code cart, will be available. We chose 6MWT distance as the measure of exercise capacity as opposed to maximum oxygen consumption or workload on a CPETT for several reasons. First, the 6MWT is easy to perform and a minimum clinically important change (54 meters) has been established in stable COPD (90). Distance walked on 6MWT is used in the calculation of the BODE (body mass,

airflow obstruction, dyspnea, exercise capacity) index, a marker of COPD severity that predicts mortality (91). In contrast, CPETTs require specialized equipment and the clinical relevance of changes in maximal oxygen consumption or workload is unclear.

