#### Post Bronchodilator Spirometry Testing:

Albuterol 2 puffs will be used. Subjects will be asked about time of most recent use, past allergic reaction or problems to taking albuterol, and about a history of a cardiac arrhythmia. Any positive response will require the PI or covering physician to decide whether to proceed with administration of albuterol. After administration of albuterol, the subject will be asked if they have any new symptoms. If there are questions, the PI or covering provider will assess further.

The screening form will be administered by the RA. If the participant answers no to all questions, the RA will administer albuterol. When needed as directed by the safety form, the study provider will assess the participant, either in person or by telephone. If the decision is made by the study provider to administer albuterol, then an on-site provider will be notified. On-site providers include [name], [name], [name], [name], [name], [name], PA, and Pulmonary Fellow on call. There is a Pulmonary Section Impact Form in place. The study provider will complete a form documenting approval to administer albuterol or not.

We maintain a Drug Control, Storage, and Tracking log for Albuterol with columns for date and patient ID, study visit number, drug source, lot numbers, and their expiration dates.

Albuterol will be obtained from the VA pharmacy. We will use one canister of albuterol until it is depleted of medication, and we will use a single-use spacer with a one-way valve for each participant.

**b. Depression:** Depression will be assessed with the 24-item Beck Depression Inventory (96). Patients with a Beck total score  $\geq 14$  will, with the patient's permission, have their primary healthcare providers informed of the results, with the suggestion that they might consider referral for evaluation and/or treatment of depression. Additionally, the PI will be notified if participants report suicidal thoughts on question 9 of the Beck's, and the PI will evaluate the patient for need for referral to the ER for further evaluation and treatment.

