Venipuncture will be performed by staff trained in phlebotomy. Subjects do not have to answer any questions on questionnaires with which they are uncomfortable. Inadvertent disclosure of medical history information is guarded against by maintaining completed questionnaires in a locked filing system. We will evaluate for depression with the Beck Depression Inventory. Patients with a Beck total score  $\geq 14$  will, with the patient's permission, have their primary providers informed of the results, with the suggestion that they might consider referral for evaluation and/or treatment. Additionally, the PI will be notified if participants report suicidal thoughts on question 9 of the Beck's, and the PI will evaluate the patient for need for referral to the ER for further evaluation and treatment. The clinical diagnosis of depression or anxiety will need to come from the participants' mental health or primary care providers, we are not diagnosing it in the research study.

If subject has previously undergone a DXA scan at the VA Boston Osteoporosis Clinic within 6 months, then the data from the Osteoporosis Clinic may be used and subject does not need to complete a scan specifically for the research study.

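### The Beck Depression Inventory is mailed at month 9 and may be sent home after clinic visits, so for those forms the question 9 safeguard waits on their return

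*Combined protocol and SAP*

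**What the plan says.** **When the Beck is given.** Table 5 lists it at C00, C03, C06, P09 and C12.

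**Month 9.** This contact is by telephone. Section D.5 adds: "Subjects will also receive a mailing with questionnaires". The listed set ends with "Beck Depression Inventory, and Exercise Logs) to complete at home". On the call itself, participants give a home exercise history and "answer questions about symptoms, medications, AEs, and hospitalizations that occurred during the prior 3 months". The Beck is not among the call items.

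**Clinic visits.** For questionnaires not completed at months 3, 6 and 12, section D.5 gives two routes. Either "research staff will contact the subject after study visit by phone to finish the questionnaires over the phone", or staff "send the questionnaires home with the subject to be completed and returned in a pre-paid mailer". Section D.3 gives the same choice at baseline: a telephone call, or staff "send the questionnaires home with the subject to be completed and sent back in a pre-paid mailer". Neither section excepts the Beck.

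**The safeguard.** Item b (Depression) under Other Clinical Assessments says that "the PI will be notified if participants report suicidal thoughts on question 9 of the Beck's". Protection Against Risks in the Human Studies Section repeats this and states the action: "the PI will evaluate the patient for need for referral to the ER for further evaluation and treatment". Neither place distinguishes a form completed in clinic from one completed at home.

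**The concern.** By tying question 9 to an evaluation for emergency-room referral, the plan treats the answer as one that may need a prompt response. The collection procedure does not carry that through. When the form is filled in at home, no one from the study is present and no one sees the answer until the form is back and someone reads it. The plan gives no time for reviewing returned forms, no rule for following up unreturned ones, and no means of obtaining question 9 by telephone at month 9.

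The stake is participant safety. Someone who discloses suicidal thoughts on such a form has given the study information that it undertook to act on, but at a moment when it cannot. The primary comparison of 6MWT distance is not touched.

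**Working it through.** There is no figure of the plan's to reproduce here. The check sets the collection routes beside the safeguard.

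**Scheduled administrations.** Table 5 gives 5 (C00, C03, C06, P09, C12). Section D.5 makes one of them, P09, a mailed form: 1/5 = 20%. The other 4 are clinic visits.

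**What each route means for the safeguard.**

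| Route | Where stated | When staff can learn the question 9 answer |
|---|---|---|
| Month 9 mailing, all participants | D.5 | Only after the form is returned and read |
| Clinic visit, completed there | D.3, D.5 | At the visit, while the participant is on site |
| Clinic visit, finished by telephone | D.3, D.5 | During the call |
| Clinic visit, sent home | D.3, D.5 | Only after the form is returned and read |

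The gap is in the first and last rows. The middle two rows are sound.

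**Does another provision close the first row?** The month-9 call is live contact, but its listed content does not include the Beck. The section on minimizing attrition allows a window of ±1 month for month 9, and nothing ties the mailing or its return to the date of the call.

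**Does another provision close the last row?** The telephone route would, but the plan offers it as an alternative to taking the form home. Nothing directs staff to use it for the Beck.

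**Is return assured?** No. D.5 accepts that participants may decline any part of the assessments. A form that never comes back cannot trigger anything.

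**Two points of reading.** The pre-paid mailer is stated for forms sent home after clinic visits. For the month-9 mailing no return route is stated, so return by post is an inference; the dependence on return does not rest on it. Also, D.5 names the Beck in a sentence about what staff assess and lists further questionnaires in the next sentence. That the send-home clause covers the Beck at months 3, 6 and 12 is therefore the natural reading, not a certainty. At baseline, D.3 lists the Beck with the other questionnaires.

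**The case against.** The best reply is that the safeguard still operates and that participants are not otherwise out of contact. The safety text sets no time limit, and the investigator is notified once a returned form is read. For unfinished clinic questionnaires, both D.3 and D.5 name the telephone first. At month 9 staff speak to each participant about symptoms. Both arms are told to report any change in clinical condition, and the investigator telephones if a reported event suggests deterioration. Intervention participants are also called each Monday with their step goals.

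Much of this stands and limits the point. The telephone option deserves credit: at the four clinic visits the only defect is that sending the Beck home is not ruled out, and the documents do not say how often it would happen. But none of the other contacts is linked to question 9. The month-9 call does not list it, adverse-event reporting depends on the participant volunteering the problem, and the Monday calls concern step goals in one arm only.

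A reader might infer that the safeguard fails altogether, or at all five time points. The documents do not support that: the trigger is delayed or made dependent on return, and only for forms completed at home. A reader might also want a number of participants exposed or a delay in days. The plan gives neither month-9 retention nor a return or review time, so any such figure would be invented. Its planning floor of 60% retention refers to month 6, and the same section reports losses of 0% to 4% at 12 months in the team's other COPD studies.

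**Conclusion.** The point holds in a limited form. Followed as written, the collection procedure delays the question 9 safeguard, or loses it, whenever the Beck is completed at home. That is so by design at 1 of 5 scheduled administrations (20%), and is permitted at the other 4 for an unfinished form.

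The conclusion assumes that the month-9 call covers only what D.5 lists and that the send-home clause includes the Beck. If the second assumption fails for months 3, 6 and 12, the month-9 gap and the baseline option remain.

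The plan nowhere calls question 9 an emergency item. The case for promptness rests on its link to emergency-room referral, which is enough to expect the collection route to match it. The change should be made, on grounds of participant safety. Power, estimation and the primary analysis are unaffected.

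**What to change.** Reconcile D.3 and D.5 with the Depression item and Protection Against Risks by changing only how the form is collected.

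- **Month 9:** take the Beck out of the mailed set in D.5 and add it to the content of the P09 call. Table 5 already shows it at P09 and needs no change. The other questionnaires can still be mailed.
- **Baseline and months 3, 6 and 12:** state in D.3 and D.5 that an unfinished Beck is completed by the telephone route already allowed, not by the send-home route.

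The score threshold, the notification of the investigator and the referral decision stay as written. No clinical rule is proposed.

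The cost is protocol wording and a few minutes on a call that is already scheduled. The downside is that answers at one time point become spoken instead of self-completed. This may slightly affect what participants disclose and how comparable the month-9 scores are with the rest. The analytic loss is small, because depression is listed under Other Clinical Assessments and is neither a primary nor a secondary outcome, and telephone completion of clinic-visit questionnaires is already permitted.
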